Twenty patients who are not surgical candidates will be offered treatment with a radio-surgical technique. Four patients will be registered in each dose group. Treatments will be initiated with 4 patients utilizing the minimum dose and observe what happens. If no DLTs are observed, then escalation to the next set of 4 patients to the next initial dose level will occur. If 1 DLT is observed, treatment of the next set of 4 patients at the same dose level will occur. If zero or 1 additional DLTs are observed, then dose escalation occurs as previously described. However, if $\geq 2/4$ or $\geq 3/8$ are observed at a given dose level the trial stops. On average, this results in between 4-5 patients being treated before escalation. The table below shows the probability of stopping giving an underlying toxicity level using this design.

Table: Probability of stopping escalation given underlying toxicity

Underlying Pr(Toxicity)	0.1	0.2	0.25	0.3	0.35	0.4	0.5	0.6	0.7	0.8	0.9
Pr(Stopping)	0.07	0.25	0.37	0.49	0.61	0.71	0.86	0.95	0.99	0.998	0.999

If a patient fails original treatment, he or she will be either kept on study for observation, or if they require retreatment, they will be taken off study.

Series II

The next series will be reached if insufficient dose limiting toxicities have occurred upon completion of the initial dose escalation series I to a total dose of 48 Gy in 4 fractions to warrant limitation of further dose escalation.

At this level, if normal tissue toxicities for SBRT have not proven to be problematic for renal lesions, then “standard” dose and fractionations will be prescribed for subsequent patients as would be used for example in Lung cancer. Given the 90% expectant local control for lung

lesions given 20 Gy in 3 fractions, we are highly anticipating reaching an efficacious dose during series II of the trial. If the 12 Gy x 4 fraction cohort is irradiated without dose limiting toxicities, then 12 additional patients will be accrued for further dose escalation following dose toxicity criteria defined below:

Based on the Linear Quadratic Model commonly used for radiobiologic comparisons, each subsequent group of four participants will receive further dose escalation using a 3 fraction regimen to increase beyond 48 Gy in 4 fractions in 20% dose equivalent increments.

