The first group of four patients at this level (Series II) will receive 48 Gy to the target volume (tumor) in 3 fractions of 16 Gy per fraction. If acute toxicity is acceptable, then the next four patients will be escalated to 54 Gy in 3 fractions of 18 Gy. Finally if a dose limit has not been reached, the last group of four patients will be treated to 60 Gy in 3 fractions of 20 Gy each.

It is important to note that dose to the normal tissues surrounding the target has not been allowed to dose escalate. Tolerance levels selected for these normal organs (see Table I. and Appendix I., are consistent with RTOG standards and normal tissue limits approved for UHCMC Protocol Case 13807 associated with Prostate Cancer with Cyberknife or Linac based SBRT irradiation.

Table I. Dose Specifications for Normal Organs (and Appendix I.)

1. Bowel – No more than 1 cc can receive 8 Gy/fx for a total of 24 Gy in 3 to 4 fractions.
2. Cord – No more than 0.3 cc can receive 6.7 Gy/fx for a total of 20 Gy in 3 to 4 fractions.
3. Stomach - No more than 1.0 cc can receive 7.3 Gy/fx for a total of 22 Gy in 3 to 4 fractions.
4. Liver – No more than 2/3 of liver volume can receive 5.7 Gy/fx for a total of 17 Gy in 3 to 4 fractions. Additionally within that volume – 800 cc should not receive more than 5.0 Gy/fx for a total of 15 Gy in 3 to 4 fractions.
5. Contralateral Kidney- No more than 5 % of the volume can receive more than 4.7 Gy/fx for a total of 14 Gy in 3 to 4 fractions.

It is thought that superior Cyberknife or Linac based SBRT treatment plans and delivery for this current cohort may be achievable without any increase in normal tissue toxicity as defined above. If this is not the case for any of the 12 patients included in the new series of cohorts and where the treatment plan has been determined to fail, the patient target volume dose will be reduced to the previous cohort dose. In no case will a dose escalation occur if the normal tissue toxicities criteria are not met in the treatment plan.

If 3 successive patients fail to meet the treatment planning criteria, the dose escalation study effort will be terminated and successive remaining patients will be treated at target dose from the previous cohort of 4 patients.

For this second series of the study, patients who fail by evidence of tumor regrowth or metastatic dissemination will not be retreated to the current dose level. However, if the subject experiences

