recurrence or progression, they will either be followed by observance; or if they require retreatment, they will be taken off study.

Radiation Toxicity:

All patients should be seen at 1, 3 and 6 months \pm 2 weeks, and then every 6 months by either the radiation oncologist or the urologist to evaluate radiation toxicities, or arranged to be seen locally if unable to return to Cleveland Medical Center with reports sent back for review. At 6 months post SBRT, the patient will be scheduled to be seen in Urology to evaluate their response to the therapy with imaging and an optional biopsy. Urinary and bowel irritation manifested as urgency, frequency, dysuria, infection and incontinence will be recorded. Medications to treat radiation side-effects will be recorded as well as dose and frequency. Acute Radiation Toxicity (<180 days from treatment date) will be documented using NCI common toxicity criteria, version 4.0. A shorter period of toxicity assessment for the purposes of dose escalation will be used. This will be done at the 1, 3 and 6 month follow-up visits after radiation therapy. More delayed short-term toxicities would be used in the final determination of the recommended Phase II dose.

Dose limiting Toxicity:

Acute Radiation Toxicity \geq grade 3 in the Gastrointestinal and renal/genitourinary categories of the common terminology criteria for adverse events 4.0 (CTCAE) will be considered dose limiting (see above). The maximum tolerated dose will be one dose level below which the adverse event, as described above, occurred (See statistical section).

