9.0 STATISTICS

Statistical Considerations

The primary goal of this study is to compare and evaluate toxicities across four varied treatment schemes using a dose escalation design with four cohorts of 4-8 patients each. Escalation to the next dose will take place if no DLT's are observed in the first four patients treated at the current dose. If 2 or more DLT's are observed in the first four patients, then escalation is stopped. If 1 DLT is observed, then four more patients are treated at the same dose, and dose escalation stops if 2 or more of these next four (3/8 of patients treated at that dose) experience a DLT. If the probability of a DLT is 40%, there is a 71% chance of stopping at the current dose, whereas if the probability of DLT is 10%, there is only a 7% chance of stopping the dose escalation.

All analyses of the data will be descriptive. Clinical and radiographic efficacy will be summarized by calculating Kaplan-Meier curves for the following: overall survival, disease-free

survival, time to local progression, time to distant failure. Data from all dose groups will be pooled in these analyses. Survival rates estimated from the Kaplan-Meier curves will be estimated with 95% confidence intervals. Rates of acute and late side effects and adverse events will be summarized as proportions, with 95% confidence intervals.

Sample Size

The number of patients studied in this trial is determined by the dose escalation strategy and the number of DLT's that are observed at each dose level. With four dose levels and cohorts of 4-8 subjects per dose, the minimum sample size is 2 and the maximum is 32. It is expected that around 20 subjects will be enrolled. This design with cohort sizes of 4-8 per dose ensures that the probability of escalating to the next dose is .93 when the probability of DLT is .1, but is only .05 when the probability of a DLT is .6.

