11.0 RISKS

Risks include those that result from the special nature of radiosurgery standard of care, including errors in giving the radiation. This may include giving radiation to normal tissue around the tumor and not to the cancer, or giving the wrong dose of radiation, either too much or too little. Any of these problems could potentially be severe, possibly even fatal. There may be risks from assigning a subject to one of the four research categories versus any one of the other three options. The research physician cannot pre-determine which category is best for any individual patient as a purpose of this study is to evaluate and compare the four options.

The use of radiation in any form is also associated with a small risk of causing another cancer, either in the portion of the body directly exposed to radiation during treatment (the target of treatment), or in other sites of the body due to low doses of scattered radiation. Depending on which category a subject is assigned, the risk may be greater or smaller for one subject than for others in the study.

Because radiosurgery for treating a kidney tumor is a very new approach, there may be other risks that we are not yet aware of, some of which could potentially be severe.

All data entered into the computer will be coded and personal identifiers will be removed. All data that can be linked to an individual will be protected and the master list will be stored off-line

and will be available only to the principal investigator or his or her designee(s). Although every effort will be made to protect and maintain confidentiality, there is a slight risk of loss of confidentiality.

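### Only acute grade 3 or higher GI and renal/GU toxicity is dose limiting, so in Series I a severe acute radiation injury in another organ, or a death from it, enters neither the escalation tally nor the MTD.

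*Combined protocol and SAP*

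**What the plan says.** - **DLT definition** (Section 6.0, Dose limiting Toxicity). Acute radiation toxicity of at least "grade 3 in the Gastrointestinal and renal/genitourinary categories of the common terminology criteria for adverse events 4.0 (CTCAE) will be considered dose limiting". No other section widens the list.
- **MTD** (same paragraph). "The maximum tolerated dose will be one dose level below which the adverse event, as described above, occurred". The event meant is the DLT just defined.
- **Series I escalation** (Section 6.0, Series I). "If no DLTs are observed, then escalation to the next set of 4 patients to the next initial dose level will occur". One DLT in four leads to four more patients at the same dose; 2 or more of 4, or 3 or more of 8, stops the trial.
- **Section 9.0** repeats the rule: "Escalation to the next dose will take place if no DLT's are observed in the first four patients treated at the current dose".
- **Table I** limits dose to organs beyond bowel, stomach and kidney. For the cord: "No more than 0.3 cc can receive 6.7 Gy/fx for a total of 20 Gy". For the liver: "No more than 2/3 of liver volume can receive 5.7 Gy/fx for a total of 17 Gy in 3 to 4 fractions".
- **Series II entry** is worded more broadly than Series I. It asks "if normal tissue toxicities for SBRT have not proven to be problematic for renal lesions", and the first step within Series II depends on acute toxicity being acceptable.
- **Section 7.0** ends a patient's own radiation if a DLT occurs.
- **Section 12.0** captures adverse events of grade 2 and above, sends serious adverse events to the Data Safety and Toxicity Committee (DSTC) and the IRB, and provides for a pause after an unanticipated event judged an unreasonable risk.

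**The concern.** The primary objective is safety, and the design delivers it through the DLT count. That count covers two organ categories, while the plan itself treats at least one organ outside them, the cord, as needing protection. Section 11.0 also warns that severe risks may exist that are not yet known. A rule confined to the expected toxicities cannot respond to an unexpected one.

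At stake is the real-time decision. If a patient at one Series I level suffers a grade 3 to 5 acute radiation injury outside the two categories, the rule as written sends the next four patients to a dose 2 Gy per fraction higher, and the MTD takes no account of the event. If the injury appears between fractions, the Section 7.0 instruction to stop that patient's radiation is not triggered either.

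**Working it through.** **1. The plan's own figures.** With X and Y the DLT counts in the first and second four patients at a level, each Bin(4, p):

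P(stop) = P(X ≥ 2) + P(X = 1) × P(Y ≥ 2)

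- p = 0.10: 0.0523 + 0.2916 × 0.0523 = 0.068 (plan: 0.07)
- p = 0.20: 0.1808 + 0.4096 × 0.1808 = 0.255 (plan: 0.25)
- p = 0.40: 0.5248 + 0.3456 × 0.5248 = 0.706 (plan: 0.71)

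The Section 6.0 table is therefore right, but its p is the rate of *counted* toxicity. Harm outside the two categories leaves P(stop) where it was.

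**2. What changes with no assumed rate.** First four patients at a level, events in different patients:

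| Counted | Outside | As written | If outside harm counted |
|---|---|---|---|
| 0 | 1 | 0/4, escalate | 1/4, treat four more |
| 0 | 2 | 0/4, escalate | 2/4, stop |
| 1 | 1 | 1/4, treat four more | 2/4, stop |

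**3. Illustration with assumed rates.** Let c be the counted rate per patient and a the outside rate. The documents give neither; a is taken over 1% to 10%. Counting both, p becomes 1 − (1 − c)(1 − a) if the two are independent, or c + a if they fall in different patients. Example: c = 0.10, a = 0.01 gives p = 0.109 or 0.110, and P(stop) = 0.0613 + 0.3084 × 0.0613 = 0.080, or 0.0624 + 0.3102 × 0.0624 = 0.082.

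The chance that the written rule escalates from a level where at least one outside injury occurred is, under independence,

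P(X = 0)[1 − (1 − a)^4] + P(X = 1)P(Y ≤ 1)[1 − (1 − a)^8].

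Example: c = 0.10, a = 0.01 gives 0.6561 × 0.0394 + 0.2916 × 0.9477 × 0.0773 = 0.047. If the events fall in different patients, put r = 1 − c − a; the chance is then (1 − c)^4 − r^4 + P(X = 1)P(Y ≤ 1) − 4cr^3(r^4 + 4cr^3), which gives 0.049.

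| c | a | P(stop) as written | P(stop) if counted | Written rule escalates with ≥ 1 outside injury |
|---|---|---|---|---|
| 0.10 | 0.01 | 0.068 | 0.080-0.082 | 0.047-0.049 |
| 0.10 | 0.02 | 0.068 | 0.094-0.097 | 0.092-0.095 |
| 0.10 | 0.05 | 0.068 | 0.140-0.150 | 0.215-0.222 |
| 0.10 | 0.10 | 0.068 | 0.233-0.255 | 0.383-0.397 |
| 0.20 | 0.01 | 0.255 | 0.273-0.278 | 0.042-0.046 |
| 0.20 | 0.02 | 0.255 | 0.292-0.301 | 0.082-0.090 |
| 0.20 | 0.05 | 0.255 | 0.348-0.372 | 0.189-0.208 |
| 0.20 | 0.10 | 0.255 | 0.444-0.492 | 0.332-0.364 |

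Each range runs from independence to different patients. The last column is before any oversight action, and it is not the chance that the final decision differs: a single outside injury, once counted, may only bring in four more patients before escalation.

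**4. Knock-on effects of counting.**

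- Clearing all four Series I levels, same rate at each, is (1 − P(stop))^4. At a = 0.01 it falls from 0.756 to 0.711-0.716 (c = 0.10), or from 0.308 to 0.272-0.279 (c = 0.20).
- Section 6.0, read literally, opens Series II if the 12 Gy × 4 cohort has no DLT. For its first four patients at c = 0.10 that chance is 0.9^4 = 0.656. Under independence it falls to 0.891^4 = 0.630 at a = 0.01, or 0.81^4 = 0.430 at a = 0.10.

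**The case against.** **Organ-specific DLTs are a legitimate choice, and Table I fixes the planned limits for cord and liver at every dose level.** An injury there may therefore say less about the next level than a GI or renal event does. This stands in part. But a planning limit is a cap, so dose beneath it can still rise with tumour dose; it governs planned dose, not observed injury; and organs without a Table I limit are not covered.

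**Other safeguards exist.** This stands, and it limits the point. A reader might infer that only a discretionary pause could prevent escalation. The documents do not show that: Section 12.0 also commits the study to an approved monitoring plan and an operations manual, neither of which is in the documents, and to DSTC and IRB oversight. The pause is also wider than it may look. The warning "Any of these problems could potentially be severe, possibly even fatal" in Section 11.0 concerns delivery errors, so such an event might be read as anticipated, whereas cord injury after correct delivery is named nowhere and fits the definition of an unanticipated event readily.

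**Not every radiation-related death is missed.** Correct. A fatal GI or renal/GU toxicity is above grade 3 and counts. Nor should the liver carry the argument: whether a liver event falls outside the GI category depends on a CTCAE grouping that the documents do not give. The cord is the safer example.

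**A delivery error is not a property of the dose level.** Fair. Under the wording proposed below such an injury could still count; recording attribution at least makes the reason visible.

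**Counting every possibly related grade 3 event would be too wide.** This also stands. Patients are poor surgical candidates with Karnofsky status as low as 60, and transient laboratory changes would produce false DLTs. The definition should be narrower than that.

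**Conclusion.** The gap is real and lies in one definition. In Series I, severe acute radiation-related injury outside the GI and renal/GU categories, or a death from it, changes neither the 2/4 or 3/8 tally nor the MTD. The safeguards elsewhere may halt the study, but none of them rewrites the escalation rule.

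Its size is not known. The decision table in step 2 needs no assumed rate; every probability for outside harm rests on an assumed rate, on equal risk across patients and on the two dependence cases shown. Nothing in the documents supports 5% or 10% over 1%.

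Two further inferences should be resisted. This is not a reporting failure: adverse events are captured and summarised as proportions with confidence intervals. Nor can one assume that the recommended Phase II dose would pick the event up later, because Section 6.0 says this only of more delayed short-term toxicities. The change is worth making, because safety is the primary objective and the cost is small if such harm is rare.

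**What to change.** Extend the DLT sentence in Section 6.0 so that, besides acute grade 3 or higher GI and renal/GU toxicity, the following are dose limiting:

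- any death at least possibly related to radiation; and
- any acute, clinically significant, non-haematological CTCAE 4.0 toxicity of grade 3 or higher in any other organ category, new or worsened from baseline and at least possibly related to radiation, excluding transient asymptomatic laboratory changes.

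Record the attribution before each escalation decision. Leave the 2/4 and 3/8 rule and the acute window unchanged. Injury appearing after that window stays outside the tally, as now.

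**Cost.** One amended sentence and an attribution record. No visit or test is added, since toxicity is already evaluated at 1, 3 and 6 months, and the Series I maximum of 32 stays. The downsides to state are:

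- slightly more stopping if such harm is rare, and substantially more if it is common (step 3), including some from events wrongly attributed to radiation;
- the affected patient's remaining fractions cease under Section 7.0;
- read literally, a lower chance of opening Series II (step 4).

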6.0 RADIATION THERAPY

Patient will have a treatment planning session for delivery of radiosurgical treatments and an immobilization device will be custom made for every patient, per standard of care. Specification of patient immobilization for each radiation treatment will conform to institutional practice.

Serum Blood Markers:

Patients will be asked to participate in ELISA blood testing just prior to and immediately following each daily radiation therapy session. Approximately 5cc of blood will be collected

within 2 hours prior to and following completion of fractionated radiation therapy to assess the levels of MIF (both MIF-1 and MIF-2) and VEGF. This whole blood will be separated into plasma and rapidly frozen at -80 C using standard procedures. At later time points, plasma samples will be thawed and subjected to an ELISA for each of the markers using commercial kits and standards. Given that survival or regrowth of tumor vasculature has been suggested to be a major determinant of radiation responses, measurement of VEGF levels prior and following radiation, these tests may give a predictive indication of tumor response.

Pending patient approval, we will also store remaining plasma samples for detection of additional cancer markers to potentially improve our ability to predict for response to therapy with new tumor markers.

Radiation Doses:

Radiation will be delivered in 4 fractions. The initial dose level will be 6 Gy per fraction to a total dose of 24 Gy in 4 fractions. Doses will be escalated at 2 Gy per fraction increments to 12 Gy per fraction to a total dose of 48 Gy. The radiation treatment planning and evaluation details are appended.

Series I:

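### The only MTD definition gives no DLT count and is never tied to the stopping rule; read literally, it can place the reported MTD below a dose that did not meet the stopping criterion

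*Combined protocol and SAP*

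**What the plan says.** The term maximum tolerated dose appears once, in Section 6.0 under Dose limiting Toxicity: "The maximum tolerated dose will be one dose level below which the adverse event, as described above, occurred (See statistical section". The sentence before it defines a DLT by timing (acute), grade (3 or higher) and organ category (gastrointestinal, renal/genitourinary). It gives no number of patients.

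The section it refers to, 9.0 Statistics, has the escalation and stopping rule, the descriptive analyses and the sample size. It does not mention the MTD. The rule is:

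- After the first four patients: "If 2 or more DLT's are observed in the first four patients, then escalation is stopped".
- With one DLT: "If 1 DLT is observed, then four more patients are treated at the same dose". Escalation then stops if at least two of the second four have a DLT, that is, at 3/8 or more.
- Section 6.0 (Series I) gives the other side: "If zero or 1 additional DLTs are observed, then dose escalation occurs as previously described". A level with 1/8 or 2/8 DLTs therefore passes.

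Series I has four levels, 24, 32, 40 and 48 Gy in four fractions: "Doses will be escalated at 2 Gy per fraction increments to 12 Gy per fraction to a total dose of 48 Gy". Series II adds three levels of 16, 18 and 20 Gy in three fractions.

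The MTD is not the last word on dose. Section 6.0 (Radiation Toxicity) adds: "More delayed short-term toxicities would be used in the final determination of the recommended Phase II dose".

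**The concern.** The MTD sentence turns on the occurrence of an event; the stopping rule turns on a count. The two part ways at any level that has a DLT and still passes. On its plain wording the sentence puts the MTD below such a level, while the rule treats that level as acceptable.

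The sentence is also silent on two outcomes: the first level stops, so that no level lies below it, or no level stops.

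At stake is one reported result. If the meaning is settled only once the DLT counts are known, the same counts can support different MTDs and the choice becomes post hoc.

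**Working it through.** **Inputs.** The stopping rule (Sections 6.0 and 9.0) and the four Series I levels (Section 6.0). The documents give no dose-toxicity curve, so every DLT rate used below, other than those in the protocol's own table, is an assumption.

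**Per-level formulas.** For DLT rate p, let P0 = (1−p)^4, P1 = 4p(1−p)^3 and P2 = 1 − P0 − P1. Then:

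- pass with no DLT: c = P0
- pass with at least one DLT (1/8 or 2/8): d = P1 × (P0 + P1)
- stop (≥2/4 or ≥3/8): s = P2 + P1 × P2

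**The protocol's own figures.** At p = 0.1, s = 0.0523 + 0.2916 × 0.0523 = 0.068 (stated 0.07). At p = 0.4, s = 0.5248 + 0.3456 × 0.5248 = 0.706 (stated 0.71). All eleven entries of the Section 6.0 table reproduce within 0.01. The stopping probabilities are sound.

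**How often a level passes with a DLT.**

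| Assumed p | d: pass with ≥1 DLT | s: stop |
|---|---|---|
| 5% | 0.1715 × 0.9860 = 0.17 | 0.02 |
| 10% | 0.2916 × 0.9477 = 0.28 | 0.07 |
| 20% | 0.4096 × 0.8192 = 0.34 | 0.25 |

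At these rates a level is more likely to pass with a DLT than to stop.

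**Two examples** (DLTs at 24, 32, 40 and 48 Gy).

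| DLTs | Below first level with a DLT | Below highest level with a DLT | Stopping rule |
|---|---|---|---|
| 0/4, 0/4, 0/4, 1/8 | 40 Gy | 40 Gy | no level in Series I stopped |
| 0/4, 1/8, 0/4, 2/4 | 24 Gy | 40 Gy | 40 Gy |

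**Series I trials that stop.** The probability of stopping somewhere is 1 − Π(c+d) over the four levels. The first-DLT reading agrees with the stopping rule only when every level before the stop was free of DLTs, which has probability Σ_k s_k × Π_{j<k} c_j.

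| Assumed rates at the four levels | Stop | Stop, no earlier DLT | First-DLT reading disagrees, share of stopped trials |
|---|---|---|---|
| 10% throughout | 24.4% | 16.0% | 8.4/24.4 = 34% |
| 5/10/15/20% | 41.9% | 22.3% | 19.6/41.9 = 47% |
| 10/20/30/40% | 89.6% | 41.2% | 48.4/89.6 = 54% |

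The highest-level reading disagrees in 0% of stopped trials, because the level that stops always has DLTs and is always the last one treated.

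**Series I trials that never stop but have a DLT at 48 Gy.** Probability = Π_{j<4}(c_j + d_j) × d_4:

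- 10% throughout: 0.8107 × 0.2763 = 22.4% of all trials
- 5/10/15/20%: 0.7797 × 0.3355 = 26.2%
- 10/20/30/40%: 0.3532 × 0.1642 = 5.8%

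Here both literal readings put the Series I MTD below 48 Gy, and the stopping rule does not. Whether that is final depends on entry to Series II, for which Section 6.0 has two gates. One is strict: "If the 12 Gy x 4 fraction cohort is irradiated without dose limiting toxicities, then 12 additional patients will be accrued". Under it these trials end at 48 Gy. The other opens Series II unless there were enough DLTs to justify limiting further escalation; under it a trial with 1/8 or 2/8 at 48 Gy could continue, and the MTD would depend on what followed.

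**The uncovered cases.** Under the same profiles, no Series I level stops in 100 − 24.4 = 75.6%, 100 − 41.9 = 58.1% and 100 − 89.6 = 10.4% of trials. The first level stops in 6.8%, 1.6% and 6.8% (s at p = 10%, 5% and 10%).

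**The case against.** The strongest reply is that the sentence should be read with its own cross-reference. The only rule in Section 9.0 that connects DLTs to dose levels is the stopping rule, so the MTD is one level below the level that stopped. This is the probable intent, and it stands. What is missing is a sentence that says so, and the inference still does not cover a trial in which no level stops or the first one does.

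A reader might infer that the protocol will report a wrong MTD in a third to a half of stopped trials. The documents do not support that. The 34% to 54% require the adverse event to mean the first DLT at any level, in a protocol that expands and escalates past such a level. Of the three readings, the other two agree in every stopped trial.

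A reader might also count the 5.8% to 26.2% as definite disagreements. They are final only under the strict Series II gate. Under that gate, moreover, 48 Gy with 1/8 did not clear its onward step, so an MTD of 40 Gy is less clearly anomalous. It remains true that 48 Gy did not meet the stopping criterion.

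Lastly, the consequence is limited. The MTD is not named in the objectives (Section 2.0) or in Section 9.0, all analyses are descriptive, and the recommended Phase II dose also draws on delayed toxicities. That limits the weight of the point but does not remove the ambiguity from a result that Section 6.0 says the trial will determine.

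**Conclusion.** The point holds as a missing link between the MTD and the stopping rule, with a literal wording that conflicts with that rule whenever a level passes with 1/8 or 2/8 DLTs. That happens at a given level with probability 0.17, 0.28 and 0.34 at assumed DLT rates of 5%, 10% and 20%. How often the reported MTD would change depends on the reading, on the assumed profile and on which Series II gate applies, so no single figure can be given.

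It would be wrong to conclude that patients would be treated at the wrong dose or that the stopping table is in error. Escalation, patients' doses and the stopping probabilities follow the Series I rule and Section 9.0, and are unaffected. The sentence should be fixed, because it defines a reported result and the remedy is nearly free. The figures cover Series I only. Series II was not modelled, because its text gives no DLT count: "If acute toxicity is acceptable, then the next four patients will be escalated to 54 Gy in 3 fractions of 18 Gy".

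**What to change.** Replace the MTD sentence in Section 6.0, and repeat it in Section 9.0, with:

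> The MTD is the dose level immediately below the level at which the stopping criterion (≥2/4 or ≥3/8 DLTs) is met. If the first level meets it, no tolerated dose is declared. If no level tested meets it, the MTD is reported as not reached and the highest level tested is stated.

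Do not restrict the sentence to Series I. The present definition is not limited to a series, and a restricted one would leave the 16, 18 and 20 Gy × 3 levels with no MTD definition. The DLT count that governs escalation within Series II, and the choice between its two entry gates, are separate matters that this sentence does not settle.

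The cost is one sentence in two places. It needs no extra patients and does not change the Series I escalation rule, its stopping probabilities or the doses given.
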